3.2. SCHEDULE OF EVENTS

Schedule of events can be found in Section 5.1 of the protocol.

3.3. CHANGES TO ANALYSIS FROM PROTOCOL

The FAS population will include subjects who received at least one dose of study treatment, and who have baseline data for at least one efficacy variable.

Descriptive statistics for electrocardiogram (ECG) parameters will not be calculated as per protocol.

Individual parameter results will be kept on site, but only the number of patients with normal, abnormal - not clinically significant (NCS) and abnormal - clinically significant (CS) results will be reported.

Potentially Clinically Significant Abnormalities (PCSA) will not be considered due to data unavailability.

The Country and US vs Non-US subgroup analyses will not be performed because of the small number of subjects from some countries.

Analyses of miRNA-124 levels in blood and tissue will be analysed and reported separately by an independent vendor and will be excluded from the final outputs and analysis conducted by IQVIA.

Additionally, pharmacokinetic (PK) results will also be reported separately by an independent vendor, but external data may be made available to IQVIA Biostatistics and the subgroup 'Week 16 ABX464-NGlu AUC0-12 level above/below 7 000 h*ng/mL' will be included in subgroup analyses, if available.

The analysis of the following secondary endpoints will not be addressed in this SAP:

- Change relative to baseline in miRNA-124 expression
- Change relative to baseline in infiltrate/histopathology (Sigmoidal) using the RHI
- IL-6, TNF α , IL-1b, IL-10 plasma concentrations
- Serum concentration of ABX464 and N-Glucuronide ABX464

Document: \\ieedc-vnasc01\BIOSdata\Abivax\ABX464\FZA92720\Biostatistics\Documentation\SAP\ABX464-103_SAP_V2.0_10MAY2021

Author: [REDACTED]

Version Number:
Version Date:

2.0
10May2021

Template No.: CS_TP_BS016 Revision 5

Reference: CS_WI_BS005

Effective Date: 01Apr2018

4. PLANNED ANALYSES

The following analyses will be performed for this study:

- Analyses for Data Safety Monitoring Board (DSMB) meetings
- Final Analysis

4.1. DATA SAFETY MONITORING BOARD (DSMB)

A DSMB will review the safety of the trial every two months during the entire study period. A DSMB charter describing the methodology and presentation of results and access to results will be provided by Abivax as a separate document.

4.2. INTERIM ANALYSIS

There will be no interim analysis for this study.

4.3. FINAL ANALYSIS

All final, planned analyses identified in this SAP will be performed by IQVIA Biostatistics following Sponsor Authorization of this SAP, Sponsor Authorization of Analysis Sets, Database Lock (DBL) and Unblinding of Treatment.

5. ANALYSIS SETS

Agreement and authorization of patients included/excluded from each analysis set will be conducted prior to the unblinding of the study. To facilitate this, a Blind Data Review (BDR) of data will be co-ordinated by the IQVIA Statistical Team Lead (STL).

Document: \\ieedc-vnasc01\BIOSdata\Abivax\ABX464\FZA92720\Biostatistics\Documentation\SAP\ABX464-103_SAP_V2.0_10MAY2021

Author: [REDACTED] Version Number: 2.0
Version Date: 10May2021

Template No.: CS_TP_BS016 Revision 5

Reference: CS_WI_BS005

Effective Date: 01Apr2018

A horizontal bar chart illustrating the percentage of respondents who have heard of various topics. The y-axis lists the topics, and the x-axis represents the percentage, ranging from 0% to 100% in increments of 10%. The bars are black with white outlines.

Topic	Percentage
Healthcare	95%
Technology	92%
Finance	88%
Politics	85%
Entertainment	82%
Science	78%
Food	75%
Sports	72%
Business	68%
Art	65%
History	62%
Geography	58%
Mathematics	55%
Chemistry	52%
Physics	48%
Biology	45%
Physics	42%
Chemistry	38%
Biology	35%
Mathematics	32%
Geography	28%
History	25%
Art	22%
Business	18%
Sports	15%
Food	12%
Science	10%
Entertainment	8%
Technology	5%
Politics	3%
Finance	2%
Healthcare	1%

Any exceptions to the analysis set assignments described in Section 5.2 will be reviewed on an individual basis.

Document: \\ieedc-vnasc01\BIOSdata\Abivax\ABX464\FZA92720\Biostatistics\Documentation\SAP\ABX464-103 SAP V2.0 10MAY2021

Author: [REDACTED]

Version Number: 2.0
Version Date: 10May2021

Template No.: CS TP BS016 Revision 5

Reference: CS WI BS005

Effective Date: 01Apr2018

5.2. ANALYSIS SETS

5.2.1. ALL PATIENTS CONSENTED ANALYSIS SET [CONS]

The All Patients Consented (CONS) Analysis Set will contain all patients who provided written informed consent (IC) to the study.

The following patients will be excluded from this Analysis Set:

- Patients who did not provide written informed consent at the screening visit

CRITERION [1]: No Written Informed Consent Provided.
DEVIATION STATUS: Major.
NOTES: 
• Data for all patients (including screen failures considered not eligible for enrollment) will be entered into the clinical study database and made available for presentation.• Data for rescreened patients are analyzed as assigned to the new patient number only. No data will be transferred from a previous data patient number to the new patient number. All baseline data required per the protocol will be collected under the new patient number.• This criterion will be tested using:
• The date that informed consent was signed, as captured on the Demography (DM) eCRF and obtained from raw.DSSTDAT_IC.

5.2.2. SAFETY ANALYSIS SET [SAF]

The Safety Analysis Set (SAF) will include all randomized patients who have received at least one dose of the study treatment. If there is any doubt whether a patient was treated or not, they will be assumed treated for the purposes of analysis. The SAF will be used for all safety analyses and patients will be analyzed as treated. Should a subject be exposed to two different treatment doses during the study, the subject will be analyzed according to the treatment received most of the time. This will be confirmed on

Document: \\ieddc-vnasc01\BIOSdata\Abivax\ABX464\FZA92720\Biostatistics\Documentation\SAP\ABX464-103_SAP_V2.0_10MAY2021

Author: [REDACTED]

Version Number:

2.0

Version Date:

10May2021

Template No.: CS_TP_BS016 Revision 5

Reference: CS_WI_BS005

Effective Date: 01Apr2018

a case-by-case basis at the BDR meeting.

The following patients will be excluded from this Analysis Set:

- Patients who have not received at least one dose of the study treatment:

CRITERION [3]: Randomized but no dose of ABX464 or Placebo Taken
DEVIATION STATUS: Major.
NOTES: 
• This criterion will be tested using the following data, as captured on the Exposure (EC) and drug accountability (DA) eCRF:
• The start date of study medication, as obtained from raw.EC.ECSTDAT.• Number of capsules dispensed and returned, as obtained from raw.DA.DAORRES4 and DAORRES5.

5.2.3. FULL ANALYSIS SET [FAS]

The Full Analysis Set (FAS) will include all patients included in the study who have received at least one dose of the study treatment, and who have baseline data for at least one efficacy variable.

The following patients will be excluded from this Analysis Set:

- All patients excluded from the SAF
- All patients who do not have baseline data for at least one efficacy variable

CRITERION [4]: Does not have baseline data for at least one efficacy variable
DEVIATION STATUS: Major.
NOTES: 
• This criterion will be tested using the following data, as captured in the eCRF and e-Diaries:
• Baseline MMS and pMMS as obtained from raw.MMS.MMSSCR and raw.PMMS.PMMSSCR, prior to first dose of study treatment. Baseline stool frequency (raw.MMS.MMSST), rectal bleeding frequency

Document: \\ieddc-vnasc01\BIOSdata\Abivax\ABX464\FZA92720\Biostatistics\Documentation\SAP\ABX464-103_SAP_V2.0_10MAY2021

Author: [REDACTED]

Version Number:

2.0

Version Date:

10May2021

Template No.: CS_TP_BS016 Revision 5

Reference: CS_WI_BS005

Effective Date: 01Apr2018

(raw.MMS.MMSRB) and endoscopic assessments (raw.MMS.MMSMA) will also be obtained from these scores.

- Baseline fecal calprotectin and CRP levels as obtained from the laboratory.
- Baseline IBDQ questionnaire completed as captured in the eDiary.

5.2.4. PER PROTOCOL ANALYSIS SET [PPAS]

The Per Protocol Analysis Set (PPAS) will include all patients in the FAS who do not have major PDs that would affect the evaluation of the primary efficacy endpoint. From a statistical analysis perspective, the reason(s) for exclusion of patients may be a PD or other factors affecting the primary efficacy outcome. PDs identified during the clinical conduct of the study, as authorized in the final PD log, will also be taken into consideration in the final assignment of patients to the analysis sets.

Reasons for exclusion are defined as:

- Insufficient essential efficacy data i.e. no MMS score at either Baseline or Week 8
- Non-compliance with the inclusion or exclusion criteria, including insufficient evidence of the study indication, i.e. MMS score < 5 (or MMS < for patients enrolled on original protocol) and endoscopy sub-score < 2 at screening
- Non-compliance with the study treatment up to Week 8 (< 80%)
- Intake of prohibited medication up to Week 8
- Non-compliance with time window up to Week 8 (+/- 7 days) (to be confirmed at CRT meeting)

Therefore, the following patients will be excluded from this Analysis Set:

- All patients excluded from the FAS.
- Patients with essential efficacy data missing or invalid:

CRITERION [5]: Insufficient Essential Efficacy Data

DEVIATION STATUS: Major.

NOTES:

Document: \\iedc-vnasc01\BIOSdata\Abivax\ABX464\FZA92720\Biostatistics\Documentation\SAP\ABX464-103_SAP_V2.0_10MAY2021

Author: [REDACTED]

Version Number:

2.0

Version Date:

10May2021

Template No.: CS_TP_BS016 Revision 5

Reference: CS_WI_BS005

Effective Date: 01Apr2018

- The primary efficacy variable is the change in MMS score from baseline to Week 8.
- This criterion will be tested using:
 - The subject's MMS scores, as captured on the MMS eCRF and obtained from raw.MMS.MMSSCR at Week 8.

- Patients with insufficient evidence of the study indication, i.e. ulcerative colitis:

CRITERION [6]: Insufficient Evidence of the Study Indication

DEVIATION STATUS: Major/No Major Impact, to be decided on a case-by-case basis at the final data review meeting.

NOTES:

- This criterion will be tested at Screening, and not meeting the following criteria will be captured on the IE eCRF by raw.IE.IECAT and IETESTCD, as well as on the MMS eCRF by raw.MMS.MMSSCR and raw.MMS.MMSMA:
 - The subject must have a clinically confirmed diagnosis of moderate to severe ulcerative colitis, with an MMS score of 5 to 9 inclusive and endoscopy sub-score of at least 2. Subjects enrolled on original protocol may have a baseline MMS score of 4.

- Patients younger than 18 or older than 75 years:

CRITERION [7]: Patients Younger than 18 or older than 75 Years

DEVIATION STATUS: Major/No Major Impact, to be decided on a case-by-case basis at the final data review meeting.

NOTES:

- Age (years) as at informed consent will be used.
- This criterion will be tested using:
 - The date of birth as captured on the Demographics (DM) eCRF and obtained from raw.DM.BRTHDATZ and raw.DM.AGE.
 - The date of informed consent as captured on the DM eCRF and obtained from

Document: \\ieddc-vnasc01\BIOSdata\Abivax\ABX464\FZA92720\Biostatistics\Documentation\SAP\ABX464-103_SAP_V2.0_10MAY2021

Author: [REDACTED]

Version Number:
Version Date:

2.0
10May2021

Template No.: CS_TP_BS016 Revision 5

Reference: CS_WI_BS005

Effective Date: 01Apr2018

raw.DM.DSSTDAT_IC.

- Patients who didn't meet the required laboratory screening criteria:

CRITERION [8]: Patient Didn't Meet Laboratory Screening Criteria

DEVIATION STATUS: Major/No Major Impact, to be decided on a case-by-case basis at the final data review meeting.

NOTES:

- The patient must meet the following laboratory screening criteria:
 - Haemoglobin $> 9 \text{ g/dL}^{-1}$
 - Absolute neutrophil count $\geq 750 \text{ mm}^{-3}$
 - Platelets $\geq 100,000 \text{ mm}^{-3}$
 - Total serum creatinine $\leq 1.3 \times \text{ULN}$ (upper limit of normal)
 - Creatinine clearance $> 90 \text{ mL min}^{-1}$ by the Cockcroft-Gault equation within 60 days prior to baseline
 - Total serum bilirubin $< 1.5 \times \text{ULN}$
 - Alkaline phosphatase, aspartate aminotransferase (AST)/serum glutamic oxaloacetic transaminase (SGOT) and alanine aminotransferase (ALT)/serum glutamic pyruvate transaminase (SGPT) $< 2 \times \text{ULN}$
- This criterion will be tested using the following data:
 - Not meeting these criteria will be captured on the IE eCRF and obtained from raw.IE.IEYN, IECAT and IETESTCD.

- Patients who didn't have documented inadequate response, no response, loss of response or an intolerance to specified alternate treatments:

• CRITERION [9]: Patient Didn't have Documented Inadequate Response, No Response, Loss of Response or an Intolerance to Specified Alternate Treatments:

DEVIATION STATUS: Major/No Major Impact, to be decided on a case-by-case basis at the final data review meeting.

Document: \\iedc-vnasc01\BIOSdata\Abivax\ABX464\FZA92720\Biostatistics\Documentation\SAP\ABX464-103_SAP_V2.0_10MAY2021

Author: [REDACTED]

Version Number:

2.0

Version Date:

10May2021

Template No.: CS_TP_BS016 Revision 5

Reference: CS_WI_BS005

Effective Date: 01Apr2018

NOTES:

- The patient must have a documented inadequate or no response, loss of response or an intolerance to at least one of the following:
 - Immunosuppressant treatment (azathioprine, 6-mercaptopurine, methotrexate)
 - TNF inhibitors
 - Vedolizumab
 - JAK inhibitors
 - Corticosteroid treatment.
 - Inadequate response, no response, loss of response is defined as:
 - Active disease or relapse despite thiopurines or methotrexate given at an appropriate dose for at least 3 months (i.e. azathioprine 2–2.5 mg/kg/day or mercaptopurine 1–1.5 mg/kg/day in the absence of leukopenia), and/or
 - Active disease despite corticosteroids treatment (prednisolone up to 0.75 mg/kg/day) over a period of 4 weeks, and/or
 - Active disease or relapse despite adequate treatment (as defined in the SmPC) with TNF inhibitors or vedolizumab, and/or
 - Active disease or relapse despite adequate treatment with JAK inhibitors over a period of at least 6 weeks.
 - This criterion will be tested using the following data:
 - Previous exposure and level of refractoriness to biological drugs, JAK inhibitors or corticosteroids as captured on the Ulcerative Colitis History (UCHX1) eCRF and obtained from raw.PREVEXP1Y and raw.UCREFRACT.
 - Active disease will be assessed by means of Criterion 6 above.
 - Not meeting this criterion will be captured on the IE eCRF and obtained from raw.IE.IEYN, IECAT and IETESTCD.
-
- Pregnant or breast-feeding patients

CRITERION [10]: Patient Exhibited Positive Pregnancy Test Result
--

DEVIATION STATUS: Major/No Major Impact, to be decided on a case-by-case basis at the final

Document: \\iedc-vnasc01\BIOSdata\Abivax\ABX464\FZA92720\Biostatistics\Documentation\SAP\ABX464-103_SAP_V2.0_10MAY2021

Author: [REDACTED]

Version Number: 2.0
Version Date: 10May2021

Template No.: CS_TP_BS016 Revision 5

Reference: CS_WI_BS005

Effective Date: 01Apr2018

data review meeting.

NOTES:

- Pregnancy will be tested with blood pregnancy tests:
 - Pregnancy test results are captured on the Pregnancy Test (PREG) eCRF and obtained from raw.PREG.HCG_LBORRES.
 - Not meeting this criterion will be captured on the IE eCRF and obtained from raw.IE.IEYN, IECAT and IETESTCD.
- Patients with a history of, or currently suffering from prohibited medical conditions as noted at Screening:

CRITERION [11]: Prohibited Previous or Current Medical Conditions

DEVIATION STATUS: Major/No Major Impact, to be decided on a case-by-case basis at the final data review meeting.

NOTES:

- All patients will be reviewed on a case-by-case basis by the Medical Advisor. A decision will be made on the effect of the potential reason for exclusion to determine if it is considered MAJOR/MINOR.
- The PD related to prohibited medical conditions as identified during the clinical conduct of the study and as authorized in the final PD log will also be considered in this decision.
- Only the data on the Medical History (MH) and Procedure History (PR) eCRF will be sent to the Medical Advisor to flag the cases that are prohibited.
- Previous or current medical conditions in the exclusion criteria include (for details see Section 4.2.2 in the protocol):
 - Crohn's Disease or presence or history of fistula, indeterminate colitis, infectious/ischemic colitis or microscopic colitis.
 - Toxic megacolon, abdominal abscess, symptomatic colonic stricture or stoma, colonic malignancy or history or imminent colectomy.
 - Colonic dysplasia, adenomatous colonic polyps or severe gastrointestinal complications.

Document: \\iedc-vnasc01\BIOSdata\Abivax\ABX464\FZA92720\Biostatistics\Documentation\SAP\ABX464-103_SAP_V2.0_10MAY2021

Author: [REDACTED]

Version Number:
Version Date:

2.0
10May2021

Template No.: CS_TP_BS016 Revision 5

Reference: CS_WI_BS005

Effective Date: 01Apr2018

- More than one episode of herpes zoster or history (single episode) of disseminated zoster.
- Active infections such as infected abdominal abscess, Clostridium difficile (stool antigen and toxin required), cytomegalovirus (CMV) (positive immunoglobulin M (IgM)), Tuberculosis (TB) and recent infectious hospitalization.
- Acute, chronic or history of clinically relevant pulmonary, cardiovascular, hepatic, pancreatic or renal functional abnormality, encephalopathy, neuropathy or unstable central nervous system (CNS) pathology such as seizure disorder, angina or cardiac arrhythmias, active malignancy or any other clinically significant medical problems as determined by physical examination and/or laboratory screening tests and/or medical history.
- Surveillance colonoscopy not defined as per European Crohn's and Colitis Organization (ECCO) guidelines.
- Acute, chronic or history of immunodeficiency or autoimmune disease.
- History of malignancy excluding patients considered cured (5 years disease free survivors).
- Previous treatment with tube feeding, defined formula diets or parenteral alimentation/nutrition within 3 weeks before the screening visit.
- Serious illness requiring systemic treatment and/or hospitalization within 3 weeks prior to baseline.
- This criterion will be tested using the following data:
 - Medical history is captured on the MH eCRF and obtained from raw.MH.MHTERM, MHSTDAT, MHENDAT and MHONGO. It will be coded as described in Section 11.
 - Procedure history is captured on the PR eCRF and obtained from raw.PR.PRTRT and PRSTDAT.
 - Not meeting these criteria will be captured on the IE eCRF and obtained from raw.IE.IEYN, raw.IE.IECAT and raw.IE.IETESTCD.

- Patients taking prohibited prior and concomitant medications:

Document: \\iedcd-vnasc01\BIOSdata\Abivax\ABX464\FZA92720\Biostatistics\Documentation\SAP\ABX464-103_SAP_V2.0_10MAY2021

Author: [REDACTED]

Version Number: 2.0
Version Date: 10May2021

Template No.: CS_TP_BS016 Revision 5

Reference: CS_WI_BS005

Effective Date: 01Apr2018

CRITERION [12]: Use of Prohibited Medication
DEVIATION STATUS: Major/No Major Impact to be decided on a case-by-case basis at the final BDR meeting.

NOTES:
 
• All patients will be reviewed on a case-by-case basis by the Medical Advisor. A decision will be made on the effect of the potential reason for exclusion to determine if it is considered MAJOR/NO MAJOR IMPACT.• The PD related to prohibited prior and concomitant medication use as identified up to Week 8 and as authorized in the final PD log, will also be taken into consideration in the decision.• The patient may not have taken the following drugs or received the following treatment within the specified period:
• Topical corticosteroids and topical 5-aminosalicylic acid preparations within 2 weeks prior to Screening.• TNF inhibitors, vedolizumab or other biologics within 8 weeks prior to the screening visit• Previous treatment with cyclosporine, tacrolimus or JAK inhibitors at least 4 weeks prior to the screening visit• Use of any investigational or non-registered product within 3 months or within 5 half-lives preceding baseline, whichever is longer, and during the study.• Illicit drug or alcohol use or dependence.• Vaccination with live components 30 days or fewer before first dose of study treatment and/or is planning to receive such vaccine during the study duration and upto 8 weeks after last dosing• Drugs that inhibit or induce CYP1A2 or inhibit UGT1A9 activity and inhibitors of OATP1B1/1B3 transporters• Previous treatment with ABX464.• This criterion will be tested using the following data:
• Use of concomitant and prior medication is captured on the Concomitant Medication

Document: \\iedc-vnasc01\BIOSdata\Abivax\ABX464\FZA92720\Biostatistics\Documentation\SAP\ABX464-103_SAP_V2.0_10MAY2021

Author: [REDACTED]

Version Number: 2.0
Version Date: 10May2021

Template No.: CS_TP_BS016 Revision 5

Reference: CS_WI_BS005

Effective Date: 01Apr2018

(CM) eCRF and obtained from raw.CM.CMTRT, CMSTDAT, CMENDAT, CMONGO and CMPRIOR. It will be coded as described in Section 12. Only the data on the CM eCRF will be sent to the MA to flag the cases that are prohibited.

- Not meeting this criterion will be captured on the IE eCRF and obtained from raw.IE.IEYN, IECAT and IETESTCD.

- Patients with unstable dose of permitted concomitant medications within the specified period prior to screening:

CRITERION [13]: Unstable Dose of Permitted Concomitant Medications

DEVIATION STATUS: Major/No Major Impact to be decided on a case-by-case basis at the final DR meeting.

NOTES:

- All patients will be reviewed on a case-by-case basis by the Medical Advisor. A decision will be made on the effect of the potential reason for exclusion to determine if it is considered MAJOR/NO MAJOR IMPACT.
- The PD related to unstable doses of permitted concomitant medication use as identified during the clinical conduct of the study and as authorized in the final PD log, will also be taken into consideration in the decision.
- Permitted concomitant medications must be a stable dose for the specified period prior to screening or baseline:
 - Oral corticosteroids - prednisone or prednisone equivalent (≤ 20 mg/day) or on beclomethasone dipropionate (≤ 5 mg/day) or on budesonide MMX (≤ 9 mg/day) for at least 2 Weeks prior to the screening visit.
 - Oral 5-aminosalicylic acid for at least 4 weeks prior to screening
 - Immunosuppressants in the form of azathioprine, 6-mercaptopurine, or methotrexate for at least 4 weeks prior to screening visit.
 - Probiotics (e.g. Culturelle® [Lactobacillus GG, i-Health, Inc.], Saccharomyces

Document: \\iedc-vnasc01\BIOSdata\Abivax\ABX464\FZA92720\Biostatistics\Documentation\SAP\ABX464-103_SAP_V2.0_10MAY2021

Author: [REDACTED]

Version Number: 2.0
Version Date: 10May2021

Template No.: CS_TP_BS016 Revision 5

Reference: CS_WI_BS005

Effective Date: 01Apr2018

boulardii for at least 2 weeks prior to the screening visit.

Antidiarrheals (e.g., loperamide, diphenoxylate with atropine) for at least 2 weeks prior to the screening visit

This criterion will be tested using the following data:
Use of concomitant and prior medication is captured on the Concomitant Medication (CM) eCRF and obtained from raw.CM.CMTRT, CMSTDAT, CMENDAT, CMONGO and CMPRIOR. Not meeting this criterion will be captured on the IE eCRF and obtained from raw.IE.IEYN, IECAT and IETESTCD.

- Patients who didn't adhere to the visit schedule:

CRITERION [14]: Non-Adherence to the Visit Schedule
DEVIATION STATUS: Major Impact for Baseline and Week 8 visits (primary efficacy end point). No Major Impact for other visits. To be confirmed at the final BDR meeting.

NOTES:

- The table below is guidance provided in the Schedule of Activities in the protocol:

Visit	Study day		
	Target	Lower limit	Upper limit
Screening	n/a	n/a	-31
Day 1 (Baseline)	1	n/a	n/a
Day 8	8	6	10
Day 29	29	27	31
Day 57	57	53	61
Day 85	85	81	89
Day 113	113	109	117
Day 120 (EOS)	120	118	122

For details on the calculation of the study day, see Section 6.1. EOS visit only applies to all premature discontinued patients and patients not taking part in maintenance study. In case of early discontinuation, the patient will be encouraged to return to the study center for the End of Study (EOS) visit within a week after last dosing.

Document: \\ieedc-vnasc01\BIOSdata\Abivax\ABX464\FZA92720\Biostatistics\Documentation\SAP\ABX464-103_SAP_V2.0_10MAY2021

Author: [REDACTED]

Version Number:
Version Date:

2.0
10May2021

Template No.: CS_TP_BS016 Revision 5

Reference: CS_WI_BS005

Effective Date: 01Apr2018

- This criterion will be tested using:
 - The name and date of visit as captured on the Date of Visit (DOV) eCRF and obtained from raw.DOV.VISDAT.
 - The visit for the patient will be flagged only if the day of the actual visit is outside the lower or upper limit. It will be discussed during the BDR meeting whether only the Week 8 and Week 16 visit non-adherence should be regarded as a major deviation.
- Overall study treatment non-compliance (< 80%) up to Week 8:

CRITERION [15]: Treatment Non-Compliance

DEVIATION STATUS: Major/No Major Impact to be decided on a case-by-case basis at the final data review meeting.

NOTES:

- Treatment compliance will be handled as described in Section 14. A patient's compliance will be assessed by considering the number of capsules issued and returned at each visit, as well as the actual number of capsules taken as recorded in the e-diary by the patient.
- This criterion will be tested as follows:
 - Number of capsules dispensed and returned as captured on the DA eCRF and obtained from raw.DA.DAORRES4 and DAORRES5.
 - Number of capsules taken as recorded in the e-diaries.

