3.1.1. Design and methodology

This phase IIb study will evaluate the efficacy and the safety of 3 dose-levels of ABX464, administered daily in improving Modified Mayo Score (MMS) in patients with moderate to severe Ulcerative Colitis at Week 8.

Eligible patients will be randomized into 4 parallel intervention/treatment groups:

Intervention/treatment Active Arm	
Group #1: 25mg qd	1 capsule of 25mg ABX464 + 1 capsule of Placebo
Group #2: 50mg qd	1 capsule of 50mg ABX464 + 1 capsule of Placebo
Group #3: 100mg qd	2 capsules of 50mg ABX464
Group #4: Placebo	2 capsules of Placebo

The study design is presented below:

At Week 16, regardless of their clinical/symptomatic response and the actual treatment/dose received, patients willing to continue the study treatment and eligible for enrollment will roll over in an Open Label Extension study (ABX464-104). In this extension study, all patients will be dosed with ABX464 50mg QD. ABX464-104 is a separate clinical protocol subject to health authorities and ethics committee approvals.

In the present induction study (ABX464-103), randomization will be stratified according to the following factors:

- 1) US versus non-US patients
- 2) patients without previous exposure to biological or JAK inhibitors versus patients with previous exposure to biological drugs or JAK inhibitors.

The proportion of patients with previous exposure to biologics or JAK inhibitors will be limited to 60%, including a maximal proportion of patients with previous treatment with vedolizumab of 20%. The maximal proportion of patients with previous exposure with JAK inhibitors will be limited to 10%.

Patients will be treated for 16 Weeks in this induction study. All endoscopies (videos) will be centrally reviewed. E-Diaries will be used to collect frequency of stools, rectal bleedings, number of capsules taken and the intake time.

From Day 1 onwards, randomized patients will be seen at the investigational site on a regular basis (cf. flow-chart).

Flexible sigmoidoscopy with rectal and sigmoidal (if the sigmoidal is inflamed) biopsies will be performed at screening, at Day 57 +/- 4 days (week 8) and at Day 113 +/- 4 days (week 16). The Day 113 measurement will only be taken if patient does not experience endoscopic improvement at Day 57 (i.e.:

endoscopy sub-score of 2 or 3).

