- Patients who are receiving immunosuppressants in the form of azathioprine, 6-mercaptopurine, or methotrexate needed to be on a stable dose for at least 4 Weeks prior to screening visit. Patients taking methotrexate also are advised to take folic acid 1 mg/day (or equivalent) supplementation if there is no contraindication;
- Patients on probiotics (e.g., Culturelle® [Lactobacillus GG, i-Health, Inc.], *Saccharomyces boulardii*) must be on stable doses for at least 2 Weeks prior to the screening visit;
- Patients on antidiarrheals (e.g., loperamide, diphenoxylate with atropine) must be on stable doses for at least 2 Weeks prior to the screening visit;
- Patients who have received tumor necrosis factor [TNF] inhibitors, vedolizumab or other biologics must have discontinued therapy at least 8 Weeks prior to the screening visit due to lack or insufficient efficacy or intolerance;
- Patients previously treated with cyclosporine, tacrolimus or JAK inhibitors must have discontinued therapy at least 4 Weeks prior to the screening visit due to lack or insufficient efficacy or intolerance;
- Patients previously treated with tube feeding, defined formula diets, or parenteral alimentation/nutrition must have discontinued treatment 3 Weeks before the screening visit and

must be able to take, orally, appropriate amount of food (calories) and liquids to maintain body weight;

- Patients with surveillance colonoscopy defined as per ECCO guidelines;
- Patients with the following hematological and biochemical laboratory parameters obtained at screening:
 - Hemoglobin > 9.0 g dL⁻¹;
 - Absolute neutrophil count \geq 750 mm⁻³;
 - Platelets \geq 100,000 mm⁻³;
 - Total serum creatinine \leq 1.3 x ULN (upper limit of normal);
 - Creatinine clearance $>$ 90 mL min⁻¹ by the Cockcroft-Gault equation within 60 days prior to baseline;
 - Total serum bilirubin $<$ 1.5 x ULN;
 - Alkaline phosphatase, AST (SGOT) and ALT (SGPT) $<$ 2 x ULN;
- Patients are able and willing to comply with study visits and procedures as per protocol;
- Patients should understand, sign and date the written voluntary informed consent form at the screening visit prior to any protocol-specific procedures are performed;
- Patients should be affiliated to a social security regimen (for French sites only);

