6.9.2. Prohibited concurrent medications

The following drugs are prohibited during the course of the study.

- Tumor necrosis factor [TNF] inhibitors, vedolizumab or others biologic therapies with a wash-out period of at least 8 Weeks prior to the screening visit;
- JAK inhibitors with a wash-out period of at least 4 Weeks prior to the screening visit;
- Topical corticosteroids and topical 5-aminosalicylic acid preparations with a wash-out period of at least 2 Weeks prior to the screening visit;
- Cyclosporine and tacrolimus with a wash-out period of at least 4 Weeks prior to the screening visit;
- Vaccination with live components during the study and up to 8 Weeks after the last dosing;
- Drugs that could interact with ABX464 should be avoided especially the CYP1A2 substrates (cf. Appendix #1). The following CYP1A2 substrates with a narrow therapeutic margin are prohibited during the whole course of the study (Clozapine, theophylline, ropinirol, warfarin and methadone). In case of concomitant treatment with ondansetron the maximal daily dose must be limited to 8 mg;
- Drugs that inhibit or induce CYP1A2 (cf. Appendix #1).
- Drugs that inhibit UGT1A9 activity and inhibitors of OATP1B1/1B3 transporters (cf. Appendix #1).
- Use of any investigational or non-registered product within 3 months or within 5 half-lives preceding baseline, whichever is longer and during the study.

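### SAP Criterion 12 words the cyclosporine, tacrolimus and JAK inhibitor wash-out so that, if applied as written, it flags correctly washed-out patients for the per-protocol set

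*SAP*

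**What the plan says.** SAP 5.2.4 defines the Per Protocol Analysis Set (PPAS) through numbered exclusion criteria. Criterion 12 covers prohibited medication. Its list opens with "The patient may not have taken the following drugs or received the following treatment within the specified period", so each bullet beneath names a forbidden exposure and its period. The bullet at issue reads "Previous treatment with cyclosporine, tacrolimus or JAK inhibitors at least 4 weeks prior to the screening visit". The bullet just above it reads "TNF inhibitors, vedolizumab or other biologics within 8 weeks prior to the screening visit", and the topical-treatment bullet before that uses the same 'within' form.

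The protocol states the wash-out as a condition to be met. Section 4.2.1 has "Patients previously treated with cyclosporine, tacrolimus or JAK inhibitors must have discontinued therapy at least 4 Weeks prior to the screening visit". Section 6.9.2 has "JAK inhibitors with a wash-out period of at least 4 Weeks prior to the screening visit" and "Cyclosporine and tacrolimus with a wash-out period of at least 4 Weeks prior to the screening visit".

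Earlier JAK inhibitor use is an expected feature of the population. SAP Criterion 9 accepts as evidence of treatment failure "Active disease or relapse despite adequate treatment with JAK inhibitors over a period of at least 6 weeks". Randomization is stratified on earlier biologic or JAK inhibitor exposure (Protocol 3.1.1, SAP 3.1), and the same sections cap JAK-experienced patients at 10%.

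**The concern.** The bullet appears to keep the protocol's 'at least 4 weeks' after the sentence was turned from a requirement into a prohibition. Under the lead-in, the forbidden exposure becomes treatment 4 or more weeks before screening. The protocol permits exactly that, provided treatment stopped by then.

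What is at stake is the make-up of the PPAS. A literal application would put in question patients who failed a JAK inhibitor and were properly washed out, a group named in the primary objective. It would also give no flag, from this bullet alone, for some patients who had not washed out. Set membership must be agreed before unblinding (SAP 5), so the written rule should say what is meant by then.

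**Working it through.** No power or alpha figure is involved. The check compares two rules, then sizes the group.

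**1. The rules.** Let s be the weeks before screening at which a course began and e the weeks before screening of its last dose (s ≥ e).
- Protocol 4.2.1 and 6.9.2: breach if e < 4.
- SAP bullet as written, on when treatment was taken: flagged if any treatment fell 4 or more weeks before screening, that is s ≥ 4.
- Bullet in the neighbours' form (within 4 weeks before screening): flagged if e < 4.

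**2. The possible cases.**

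| Course | Protocol | SAP as written | 'Within' form |
|---|---|---|---|
| s ≥ 4, e ≥ 4 (stopped in time) | compliant | flagged | not flagged |
| s ≥ 4, e < 4 (longer course, stopped late) | breach | flagged | flagged |
| s < 4, e < 4 (whole course inside the window) | breach | not flagged | flagged |

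The written bullet is wrong in the first and third rows and reaches the right answer in the second. The 'within' form matches the protocol in all three, taking a stop at exactly 4 weeks as compliant.

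**3. Two examples.** Criterion 9 requires at least 6 weeks on a JAK inhibitor to show failure. A patient who took it for 6 weeks and stopped 1 week before screening has e = 1 and s = 6 + 1 = 7: a breach, and flagged. A patient who could not tolerate it, started 3 weeks before screening and stopped 1 week before, has s = 3 and e = 1: a breach, and not flagged by this bullet.

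**4. If the bullet is read as referring to the last dose.** The flag then becomes e ≥ 4. At e = 1, 2, 3 and 3.9 weeks the protocol finds a breach and the bullet is silent. At e = 4, 4.1, 8 and 52 weeks the patient complies and the bullet flags. The rules disagree at all eight values. This reading needs 'last dose' to be supplied, because the bullet speaks only of previous treatment.

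**5. Evidence that this is a slip.** Criterion 11 converts a similar requirement correctly: the protocol's stop of tube feeding and similar nutrition 3 weeks before screening becomes a prohibition on such treatment within 3 weeks of screening.

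**6. Size.** Inputs are the 10% cap and the 244 planned patients (Protocol 3.1.1). 0.10 × 244 = 24.4, so at most about 24 JAK-experienced patients. Spread evenly, 24.4 / 4 = 6.1 per arm. The documents give no number for past cyclosporine or tacrolimus users.

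**The case against.** A reader might infer that the rule is a clean reversal, so that every true wash-out breach passes unnoticed. The documents do not support that, for three reasons.

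- The bullet refers to treatment, not last dose. It still flags a late stopper whose course began 4 or more weeks before screening. Only short courses lying wholly inside the window are missed.
- Those cases have other routes to detection. Non-compliance with the eligibility criteria is its own PPAS exclusion reason (SAP 5.2.4) and is classed as major in Protocol 9.1.1. Criterion 12 also draws on the inclusion/exclusion eCRF and the final deviation log. Prohibited intake up to Week 8 is listed separately.
- No exclusion is automatic. The Medical Advisor reviews each patient, and the blind data review decides whether the impact is major. Excluding every past JAK inhibitor user would contradict Criterion 9 and the stratification, so an informed reviewer would probably see the intended meaning.

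All of this stands, and it limits the consequence. It does not make the wording right. SAP 5.2.4 sends the Medical Advisor only the concomitant medication eCRF data for flagging, and Protocol 5.2.1 has sites record UC medication with no time limit, so old, compliant courses can appear there and meet the literal bullet. The inclusion/exclusion eCRF helps only if the breach was recorded on it.

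**Conclusion.** The bullet contradicts Protocol 4.2.1 and 6.9.2, the form of its neighbours and the sense of Criterion 9. It is a genuine wording error in a prespecified exclusion rule, of modest weight.

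The figure of about 24 JAK-experienced patients is a ceiling, not a forecast. It assumes that the cap is filled, that all these patients were properly washed out and that the bullet is applied literally. About 6 per arm further assumes an even spread. That is uncertain, because stratification is on biologic or JAK exposure combined and US patients are not randomized to 100 mg (SAP 3.1).

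A reader might also infer a threat to the main result, since SAP 15.1.3 runs the primary analysis on both the Full Analysis Set (FAS) and the PPAS. However, Protocol 9.2 places efficacy analysis in the FAS, and SAP 15.1.4.1 lists the PPAS run as a sensitivity analysis. FAS membership and the ordered dose tests in the FAS are untouched. The effect is confined to the PPAS and to the summaries and secondary analyses repeated on it. Nothing in the documents shows that any patient was misclassified, or that carry-over altered anyone's Modified Mayo Score.

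**What to change.** Before the blind data review assigns the PPAS, reconcile this Criterion 12 bullet with Protocol 4.2.1 and 6.9.2. Restate it as exposure to these drugs within the protocol's wash-out period prior to the screening visit, in the form of the two bullets above it, and align any review listing built from it. No clause reaching to Week 8 is needed: the PPAS exclusion reasons at the start of SAP 5.2.4 already cover prohibited intake up to that visit, and the neighbouring bullets carry no such clause.

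The cost is one line of SAP text and a check of the matching listing. No data are added, no analysis changes and the protocol's wash-out is left as it is.
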